Protocol Number: SGN22E-001

Version: Amendment 9; 15-Feb-2023

Protocol Title: A single-arm, open-label, multicenter study of enfortumab vedotin (ASG-22CE) for treatment of patients with locally advanced or metastatic urothelial cancer who previously received immune checkpoint inhibitor (CPI) therapy.

Study Name EV-201

Investigational Drug: Enfortumab vedotin (ASG-22CE)

Phase: 2

IND Number: 116360

EudraCT Number 2017-003479-78

Study Sponsor: Seagen Inc.
[name]

IND Sponsor: Astellas Pharma Global Development, Inc. (APGD)
[name]

Medical Monitor: PPD [REDACTED] MD, PhD
Seagen Inc.
Tel: PPD [REDACTED]
E-mail: PPD [REDACTED]

SAE Email or Fax: See email or fax number(s) specified on the SAE report form.

This document contains information proprietary to Seagen Inc. The information is being provided to you for the purpose of conducting a clinical trial for Seagen Inc. You may disclose the contents of this document to study personnel under your supervision and to your Institutional Review Board (IRB) or Ethics Committee (EC) for the same purpose. You may not disclose the contents of this document to any other party, unless government regulations or laws require such disclosure, without prior written permission from Seagen Inc. Any supplemental information that may be added to this document is proprietary to Seagen Inc. and should be handled using the disclosure procedure described above.

PROTOCOL SYNOPSIS

Protocol Number SGN22E-001	Product Name Enfortumab vedotin (ASG-22CE)
Version Amendment 9; 15-Feb-2023	Study Sponsor Seagen Inc. [name]
Phase 2	IND Sponsor Astellas Pharma Global Development, Inc. (APGD) [name]

Protocol Title

A single-arm, open-label, multicenter study of enfortumab vedotin (ASG-22CE) for treatment of patients with locally advanced or metastatic urothelial cancer who previously received immune checkpoint inhibitor (CPI) therapy.

Study Objectives

Primary:

- To determine the antitumor activity of single-agent enfortumab vedotin as measured by confirmed objective response rate (ORR) in patients with locally advanced or metastatic urothelial cancer who have previously received systemic therapy with a CPI and either previously received platinum-containing chemotherapy or are platinum-naïve and cisplatin-ineligible

Secondary:

- To assess duration of response (DOR)
- To assess disease control rate (DCR)
- To assess progression-free survival (PFS)
- To assess overall survival (OS)
- To assess the safety and tolerability of enfortumab vedotin
- To assess the pharmacokinetics (PK) of enfortumab vedotin
- To assess the incidence of antitherapeutic antibodies (ATA)

Additional:

- To explore potential correlations between biomarkers and clinical outcomes
- To evaluate the treatment effect of enfortumab vedotin on quality of life (QoL)

Study Population

The population to be studied includes patients with locally advanced or metastatic urothelial cancer who previously received therapy with CPI, with measurable disease according to Response Evaluation Criteria in Solid Tumors (RECIST) Version 1.1. Patients who received CPI therapy in the neoadjuvant/adjuvant setting and had recurrent or progressive disease (PD) either during therapy or within 3 months of therapy completion are eligible. Patients must also be either:

- 1) Platinum-treated (Cohort 1): Patients who received prior treatment with platinum-containing chemotherapy defined as those who received platinum in the adjuvant/neoadjuvant setting and had recurrent or progressive disease within 12 months of completion OR received treatment with platinum in the locally advanced (defined as unresectable with curative intent) or metastatic setting;

OR

- 2) Platinum-naïve and cisplatin ineligible (Cohort 2): Patients who have not received prior platinum-containing or other chemotherapy in the locally advanced or metastatic setting and are ineligible for treatment with cisplatin at time of enrollment. Patients who received platinum in the adjuvant/neoadjuvant setting and did not progress within 12 months of completion will be considered platinum-naïve.

Patients must have PD during or following their most recent therapy. Eligible patients must be ≥ 18 years of age, and legally an adult according to local regulation. Patients must have an Eastern Cooperative Oncology Group (ECOG) performance status score of ≤ 1 for Cohort 1, or ECOG ≤ 2 for Cohort 2. Patients must have an anticipated life expectancy of ≥ 3 months as assessed by the investigator. Patients must have adequate baseline hematologic, hepatic, and renal function.

Patients must not have ongoing sensory or motor neuropathy (Grade 2 or higher), or active central nervous system metastases. Patients must not have been previously enrolled in an enfortumab vedotin study or previously treated with other monomethyl auristatin E (MMAE)-based antibody-drug conjugates (ADCs). There are no limits for prior lines of therapy, including taxanes. Patients must not have a history of another malignancy within 3 years, or any evidence of residual disease from a previously diagnosed malignancy. Patients are also excluded if they are currently receiving systemic antimicrobial treatment for active infection or high dose steroids. Patients with uncontrolled diabetes are excluded. Uncontrolled diabetes is defined as hemoglobin A1C (HbA1c) $\geq 8\%$ or HbA1c 7– $<8\%$ with associated diabetes symptoms (polyuria or polydipsia) that are not otherwise explained. Patients must not have uncontrolled tumor-related bone pain or impending spinal cord compression. Patients requiring pain medication must be on a stable regimen at the time of enrollment (a minimum of 2 weeks).

Number of Planned Patients

Approximately 200 patients will be enrolled in this study, including approximately 100 or more platinum-treated patients (Cohort 1), and up to approximately 100 platinum-naïve and cisplatin-ineligible patients (Cohort 2).

Study Design

This is a single-arm, open-label, multicenter trial designed to assess the efficacy and safety of enfortumab vedotin as a single agent in locally advanced or metastatic urothelial cancer patients who have previously received systemic therapy with a CPI. For the purpose of this study a CPI is defined as a programmed cell death protein 1 (PD-1) inhibitor or programmed death-ligand 1 (PD-L1) inhibitor (including, but not limited to: atezolizumab, pembrolizumab, durvalumab, avelumab, and nivolumab). Patients must either have received prior treatment with platinum-containing chemotherapy (Cohort 1) or received no prior treatment with platinum-containing or other chemotherapy and are ineligible for treatment with cisplatin at time of enrollment (Cohort 2).

Enfortumab vedotin at a dose of 1.25 mg/kg will be administered as an intravenous (IV) infusion over approximately 30 minutes on Days 1, 8, and 15 of each 28-day cycle. Patients will continue to receive study treatment until disease progression, unacceptable toxicity, investigator decision, consent withdrawal, start of a subsequent anticancer therapy, pregnancy, or study termination by the sponsor. After discontinuation of study treatment, patients will be followed every 8 weeks (± 1 week) for response assessments, ECOG performance status, and physical exams. After 1 year of on study, the frequency of follow-up exams including response assessments will be reduced to every 12 weeks (± 1 week). Patients that have progressed or begun subsequent anticancer therapy will be contacted every 8 weeks (± 1 week) up to 1 year on study, and every 12 weeks (± 1 week) thereafter to obtain information on subsequent anticancer therapy, and survival status until death, study closure, or withdrawal of consent, whichever occurs first. The study will be closed 5 years after enrollment of the last patient, or when no patients remain in long-term follow-up, whichever occurs first. Additionally, the sponsor may terminate the study at any time.

On a periodic basis, an independent data monitoring committee (IDMC) will monitor the safety of patients participating in this trial. The IDMC will be responsible for evaluating the results of safety analyses and will make recommendations to the sponsor.

An ongoing real-time review of patient safety and serious adverse events (SAEs) will also be conducted by the sponsor's Drug Safety Department.

Test Product, Dose, and Mode of Administration

Enfortumab vedotin 1.25 mg/kg will be administered as an IV infusion over approximately 30 minutes on Day 1, 8, and 15 of each 28-day cycle.

Duration of Treatment

Patients may continue on study treatment until disease progression, unacceptable toxicity, investigator decision, consent withdrawal, start of a subsequent anticancer therapy, pregnancy, or study termination by the sponsor.

Efficacy Assessments

Measures of anticancer activity will be assessed by computed tomography (CT) scans with contrast approximately every 8 weeks (± 1 week). After 1 year on study, response assessments will be reduced to every 12 weeks (± 1 week). The schedule of response assessments should not be adjusted for dose delays/interruptions or other reasons for changes in the timing of a patient's study activities; timepoints for response assessments should be calculated from Cycle 1 Day 1 during treatment. For patients who cannot receive CT scans with contrast, other protocol-specified imaging methods may be used. Patients must be evaluated using the same imaging method throughout the study for efficacy assessments. CT scans with contrast at the minimum will include the chest, abdomen, and pelvis. Other regions should be scanned if the patient has known or suspected disease in that region. Responses (complete response [CR] or partial response [PR]) will be confirmed with repeat scans 4 weeks ($+1$ week window) after first documentation of response. The determination of antitumor activity will be based on confirmed objective response assessments as defined by RECIST Version 1.1. Response and progression will be assessed by an independent review facility (IRF). The investigator will make treatment decisions based on site assessments of scans by RECIST.

Patients who discontinue study treatment for reasons other than objective disease progression by RECIST will continue to receive scans 8 weeks (± 1 week) after the previous response assessment scan and every 8 weeks (± 1 week) following the previous scan thereafter. After 1 year on study the frequency of response assessments will be reduced to every 12 weeks (± 1 week). The tumor assessments will continue until the patient has radiologically-confirmed progression per the investigator, initiates a new anticancer therapy, dies, withdraws consent, or the study closes, whichever comes first.

Pharmacokinetic and ATA Assessments

Blood samples for PK and ATA will be collected throughout the study. Qualified or validated assays will be used to measure the concentrations of enfortumab vedotin ADC, total antibody (TAb), and MMAE in serum or plasma and assess ATA.

Biomarker Assessments

Samples for exploratory biomarkers will be collected at protocol-specified timepoints. Biomarker assessments will not be used for patient selection. Biomarker assessments in tumor tissue may include, but will not be limited to, tumor expression of Nectin-4 protein, messenger ribonucleic acid (mRNA) expression, markers of disease subtype, and markers of the immune microenvironment in tumor. Assessments in blood samples may include, but will not be limited to, markers of immune function, including abundance and phenotype of immune cell subsets, circulating tumor DNA (ctDNA), and abundance of cytokines. Methods of analysis may include immunohistochemistry (IHC), next generation sequencing, polymerase chain reaction (PCR), mutation and gene expression profiling, T-cell receptor beta chain sequencing, flow cytometry, and immunoassays.

Safety Assessments

Safety assessments will be based on the information collected through the safety surveillance process and will include the data from recorded adverse events (AEs) including SAEs, recording of concomitant medication, physical examination findings, cardiac monitoring, and laboratory tests.

Quality of Life Assessments

Patient reported outcomes (PRO) assessments will be used to obtain QoL information at protocol-specified timepoints. The following validated tools will be used: European Organisation for Research and Treatment of Cancer (EORTC) Quality of Life Questionnaire (QLQ-C30) and EuroQol 5-dimensions (EQ-5D).

Statistical Methods

Analysis for primary endpoint:

The primary endpoint of this study is the confirmed ORR per IRF. The ORR is defined as the proportion of patients with confirmed CR or PR according to RECIST Version 1.1. The ORR per IRF and its exact 2-sided 95% confidence interval (CI) using the Clopper-Pearson method ([Clopper 1934](#)) will be calculated.

There are 2 cohorts of CPI-treated patients in the study: Cohort 1) platinum-treated patients as defined in the study population above, and Cohort 2) platinum-naïve and cisplatin-ineligible patients also defined in the study population above. The primary endpoint will be analyzed separately for each cohort and may be analyzed for all patients, combining both Cohorts 1 and 2.

The primary analysis on Cohort 1 (platinum-treated patients) will be conducted when enrollment is completed in Cohort 1, and all patients in the cohort have been followed for at least 6 months, or have discontinued from study, or had 30 days safety follow-up after PD, whichever comes first. Analysis for Cohort 2 will occur at 4 timepoints: 1) at the time of analysis of Cohort 1, 2) when approximately 50 patients in Cohort 2 have had the opportunity to be followed for approximately 8 months from the first dose of enfortumab vedotin, 3) when approximately 70 patients in Cohort 2 have had the opportunity to be followed for approximately 8 months from the first dose of enfortumab vedotin, and 4) when all patients in Cohort 2 have had the opportunity to be followed for approximately 8 months from the first dose of enfortumab vedotin. All patients may also be analyzed at the time of analysis of Cohort 1 and/or Cohort 2.

The primary analysis of efficacy endpoints will be based on the full analysis set, including all patients who enrolled and received any amount of enfortumab vedotin. At the time of the interim analyses for Cohort 2, additional analyses of efficacy endpoints will be performed based on the efficacy evaluable set, including all patients in the full analysis set who started treatment with enfortumab vedotin at least 8 months before the analysis data cutoff.

Sample size:

The study is designed to estimate the confirmed ORR in patients receiving enfortumab vedotin and to detect an improvement in the ORR compared with a historical response rate of 10%. Approximately 200 patients will be enrolled in this study to ensure collection of sufficient efficacy and safety data, including approximately 100 or more platinum-treated patients (Cohort 1), and up to approximately 100 platinum-naïve and cisplatin-ineligible patients (Cohort 2). Using the estimate of approximately 100 patients Cohort 1, the study will have 98% power to detect a 15% increase in ORR from 10% to 25% and 81% power to detect a 10% increase in ORR from 10% to 20%, at one-sided significant level of 0.025, based on exact methods using EAST®, Version 6.0, by Cytel Inc.

The confirmed ORR and 95% exact CI in Cohort 2 will be summarized at 4 timepoints: 1) at the time of analysis of Cohort 1, 2) when approximately 50 patients in Cohort 2 have had the opportunity to be followed for approximately 8 months from the first dose of enfortumab vedotin, 3) when approximately 70 patients in Cohort 2 have had the opportunity to be followed for approximately 8 months from the first dose of enfortumab vedotin, and 4) when all patients treated in Cohort 2 have had the opportunity to be followed for approximately 8 months from the first dose of enfortumab vedotin.

For illustration purposes, below is the summary of expected 95% CIs for Cohort 2 at various analysis timepoints, assuming a 30% observed ORR:

Number of Patients	Expected 95% Confidence Interval
N=20	12%–54%
N=50	18%–45%
N=70	20%–42%
N=100	21%–40%

TABLE OF CONTENTS

PROTOCOL SYNOPSIS	2
LIST OF ABBREVIATIONS AND DEFINITIONS OF TERMS	10
1 INTRODUCTION	12
1.1 Urothelial Cancer	12
1.2 Second-Line Therapy Options for Metastatic Urothelial Cancer	13
1.3 Nectin-4	14
1.4 Nectin-4 as a Target in Metastatic Urothelial Cancer	14
1.5 Enfortumab Vedotin	15
1.6 Rationale for Enfortumab Vedotin in Metastatic Urothelial Cancer, Clinical Safety and Efficacy	15
2 OBJECTIVES	17
2.1 Primary Objective	17
2.2 Secondary Objectives	17
2.3 Additional Objectives	17
2.4 Endpoints	18
2.4.1 Primary Endpoint	18
2.4.2 Secondary Endpoints	18
2.4.3 Additional Endpoints	18
3 INVESTIGATIONAL PLAN	18
3.1 Summary of Study Design	18
3.2 Discussion and Rationale for Study Design	20
3.2.1 Method of Assigning Patients to Treatment Groups	21
3.2.2 Rationale for Selection of Doses	21
3.2.3 Blinding	22
4 STUDY POPULATION	22
4.1 Inclusion Criteria	22
4.2 Exclusion Criteria	25
4.3 Removal of Patients From Therapy or Assessment	26
4.3.1 Discontinuation of Study Treatment	26
4.3.2 Patient Withdrawal From Study	27
5 TREATMENTS	27
5.1 Treatments Administered	27
5.2 Investigational Study Drug	27
5.2.1 Description	27
5.2.2 Dose and Administration	27
5.2.3 Dose Modifications	28
5.2.4 Storage and Handling	31
5.2.5 Packaging and Labeling	31
5.2.6 Preparation	31
5.3 Concomitant Therapy	31
5.3.1 Required Concomitant Therapy	31
5.3.2 Allowed Concomitant Therapy	31
5.3.3 Prohibited Concomitant Therapy	32
5.4 Management of Adverse Reactions	32
5.4.1 Management of Infusion Reactions	32
5.4.2 Management of Hyperglycemia	33
5.4.3 Management of Rash Related to Enfortumab Vedotin	33

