4 STUDY POPULATION

All relevant medical and non-medical conditions should be taken into consideration when deciding whether this protocol is suitable for a particular patient. Patients must meet all of the enrollment criteria to be eligible for this study. Eligibility criteria may not be waived by the investigator and are subject to review in the event of a good clinical practice audit and/or health regulatory authority inspection.

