4.2 Exclusion Criteria

1. Ongoing sensory or motor neuropathy Grade ≥ 2 .
2. Active central nervous system (CNS) metastases. Patients with treated CNS metastases are permitted on study if all the following are true:
 - CNS metastases have been clinically stable for at least 6 weeks prior to screening and baseline scans show no evidence of new or enlarged metastasis
 - If requiring steroid treatment for CNS metastases, the patient is on a stable dose ≤ 20 mg/day of prednisone or equivalent for at least 2 weeks
 - Patient does not have leptomeningeal disease
3. Ongoing clinically significant toxicity (Grade 2 or higher) associated with prior treatment (including systemic therapy, radiotherapy or surgery). Patients with \leq Grade 2 hypothyroidism or panhypopituitarism related to treatment with PD-1 and PD-L1 inhibitors may be enrolled. Patients on hormone replacement therapy may be enrolled if on a stable dose. Patients with \geq Grade 3 immunotherapy-related hypothyroidism or panhypopituitarism are excluded. Patients with immunotherapy related myocarditis, colitis, uveitis, or pneumonitis are excluded. Patients with other immunotherapy related adverse events requiring high doses of steroids (>20 mg/day of prednisone or equivalent) are excluded.
4. Prior enrollment in an enfortumab vedotin study or prior treatment with other MMAE-based ADCs.
5. History of another malignancy within 3 years before the first dose of study drug, or any evidence of residual disease from a previously diagnosed malignancy. Patients with nonmelanoma skin cancer, localized prostate cancer treated with curative intent with no evidence of progression, low-risk or very low-risk (per standard guidelines) localized prostate cancer under active surveillance/watchful waiting without intent to treat, or carcinoma in situ of any type (if complete resection was performed) are allowed.
6. Currently receiving systemic antimicrobial treatment for active infection (viral, bacterial, or fungal) at the time of first dose of enfortumab vedotin. Routine antimicrobial prophylaxis is permitted.
7. Patients with a positive hepatitis B surface antigen and/or antihepatitis B core antibody. Patients with a negative polymerase chain reaction (PCR) assay are permitted with appropriate antiviral prophylaxis.

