8. Active hepatitis C infection or known human immunodeficiency virus (HIV) infection. Patients who have been treated for hepatitis C infection are permitted if they have documented sustained virologic response of ≥ 12 weeks.
9. Documented history of a cerebral vascular event (stroke or transient ischemic attack), unstable angina, myocardial infarction, or cardiac symptoms (including congestive heart

failure) consistent with New York Heart Association Class III-IV (see [Appendix C](#)) within 6 months prior to the first dose of enfortumab vedotin.

10. Radiotherapy or major surgery within 2 weeks prior to first dose of study drug.
11. Chemotherapy, biologics, investigational agents, and/or antitumor treatment with immunotherapy that is not completed 2 weeks prior to first dose of study drug.
12. Known hypersensitivity to enfortumab vedotin or to any excipient contained in the drug formulation of enfortumab vedotin (including histidine, trehalose dihydrate, and polysorbate 20).
13. Patients with active keratitis or corneal ulcerations. Patients with superficial punctate keratitis are allowed if the disorder is being adequately treated in the opinion of the investigator.
14. Other underlying medical condition that, in the opinion of the investigator, would impair the ability of the patient to receive or tolerate the planned treatment and follow-up.
15. Patients with uncontrolled diabetes. Uncontrolled diabetes is defined as hemoglobin A1c (HbA1c) $\geq 8\%$ or HbA1c $7-8\%$ with associated diabetes symptoms (polyuria or polydipsia) that are not otherwise explained.
16. Uncontrolled tumor-related bone pain or impending spinal cord compression. Patients requiring pain medication must be on a stable regimen at the time of enrollment (a minimum of 2 weeks).

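### The synopsis excludes patients on high dose steroids, but the governing list in Section 4.2 has no general steroid exclusion, so a patient above the Section 5.3.2 chronic cap can pass its steroid criteria

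*Protocol*

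**What the plan says.** The Study Population paragraph of the protocol synopsis gives the exclusion as "Patients are also excluded if they are currently receiving systemic antimicrobial treatment for active infection or high dose steroids". It attaches no indication, dose or duration to the steroid part.

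Section 7.1 makes the Section 4 criteria the test for enrollment, and Section 4 adds that "Eligibility criteria may not be waived by the investigator". Within Section 4.2:

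- Criterion 6 is the counterpart of the synopsis sentence. It reads "Currently receiving systemic antimicrobial treatment for active infection (viral, bacterial, or fungal) at the time of first dose of enfortumab vedotin" and then permits routine prophylaxis. Steroids do not appear.
- Criterion 2 allows treated CNS metastases under conditions, one of which begins "If requiring steroid treatment for CNS metastases, the patient is on a stable dose"; that dose may not exceed 20 mg/day.
- Criterion 3 ends with "Patients with other immunotherapy related adverse events requiring high doses of steroids (>20 mg/day of prednisone or equivalent) are excluded".

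Section 4.1 has no steroid criterion.

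For patients on study, Section 5.3.2 permits chronic prednisone or equivalent up to 20 mg/day. Higher doses are allowed for a limited time for acute conditions that arise during the study. Section 5.3.3, on prohibited therapy, does not mention steroids.

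**The concern.** The synopsis and the operative list do not select the same patients. A site working from Section 4.2 could enroll someone whom the synopsis excludes and whose background treatment Section 5.3.2 does not allow on the first dosing day.

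The stake is safety consistency. SAP Section 7.6.1.1 lists hyperglycemia as an adverse event of special interest. Protocol Section 1.6 reports one treatment-related death with serious hyperglycemia by the phase 1 data cut-off and two more soon after. Section 5.4.2 itself says that steroid use may call for extra glucose monitoring.

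There is also a reporting consequence. SAP Section 7.3 counts exemptions from the eligibility criteria as important protocol deviations. With no steroid criterion in 4.2 for this patient, the enrollment would not clearly be captured as one.

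**Working it through.** No sample size, power or rate enters this point, and the plan states no figure to reproduce. The check sets the provisions side by side and follows one case through them.

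**Threshold.** The synopsis does not define high dose. Criterion 3 puts it at more than 20 mg/day prednisone or equivalent, and the same 20 mg/day is the limit in criterion 2 and the chronic cap in 5.3.2. Reading the synopsis at that threshold is an inference, though all three provisions point to it.

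**Case.** A patient has taken prednisone 30 mg/day long term for a pre-existing airway or inflammatory disease. The disease is unrelated to CNS metastases, prior cancer treatment or immunotherapy.

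1. Synopsis: currently on high dose steroids (30 > 20), so excluded.
2. Criterion 2: steroids are not for CNS metastases, so it does not apply.
3. Criterion 3, last sentence: no immunotherapy-related event, so it does not apply.
4. Criterion 3, first sentence: this excludes ongoing clinically significant toxicity of Grade 2 or higher from any prior treatment, including radiotherapy and surgery. The condition is not such a toxicity, so it does not apply.
5. Criterion 6: concerns antimicrobials only.
6. Criterion 16: concerns uncontrolled tumor-related bone pain and impending cord compression, so it does not apply.
7. Criterion 14: "Other underlying medical condition that, in the opinion of the investigator, would impair the ability of the patient to receive" or tolerate treatment. The investigator may use it, but it depends on judgement about a condition and sets no steroid dose.
8. Section 5.3.2 on Day 1: 30 mg/day is above the chronic limit of 20 mg/day. A long-standing condition did not arise during the study, so the higher-dose allowance does not help.
9. Section 5.3.3: steroids are not listed, so mandatory discontinuation does not follow.

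The patient is excluded at step 1, passes every rule-based criterion in steps 2 to 6, and is outside 5.3.2 at step 8.

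**Is this only synopsis shorthand?** The other exclusions in that synopsis paragraph each have a counterpart of the same scope in 4.2: neuropathy (1), CNS metastases (2), prior enfortumab vedotin study or MMAE conjugate (4), other malignancy (5), antimicrobials (6), diabetes (15), bone pain and cord compression (16). High dose steroids is the exception. The amendment summaries record no decision to drop a general steroid criterion.

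**The case against.** The best reply is that the synopsis abbreviates. It also leaves out the CNS sub-conditions and the definition of cisplatin ineligibility, and high doses of steroids do appear, with a number, in criterion 3. Section 7.1 tells sites which text controls, and nothing shows that the sponsor intended a general exclusion. On this view the synopsis could simply be narrowed to the two indications. That would reconcile the synopsis with 4.2, but 4.2 would still admit the patient above and leave them over the 5.3.2 cap on Day 1. The mismatch between entry and on-study rules does not depend on how the synopsis is read.

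The second reply, that the risk is already reduced, largely stands. Criterion 15 excludes uncontrolled diabetes by HbA1c. Section 5.4.2 requires a glucose check before each dose and a hold above 250 mg/dL. Section 6.1 requires local laboratory review before dosing. Eligibility confirmation (Appendix A) and sponsor approval (Section 9.3.1.7) add a second look, but they check against the same criteria.

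Two stronger readings go too far:

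- A reader might infer that only general, discretionary controls stand at entry. The first sentence of criterion 3 and criterion 16 are specific rules that remove several conditions for which steroids might be given.
- A reader might infer that anyone who starts a short high-dose course before Day 1 is outside 5.3.2. That section does not define when the study begins for this purpose. Consent falls within a screening window opening at Day -28, so an acute condition arising between consent and Day 1 can reasonably be read as covered by the limited-duration allowance.

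**Conclusion.** The inconsistency holds in a narrow form. Section 4.2 lacks the general steroid exclusion that the synopsis states, and the patients clearly affected are those on chronic prednisone above 20 mg/day for a pre-existing condition unrelated to CNS metastases, immunotherapy, prior-treatment toxicity, cord compression or uncontrolled bone pain. This rests on reading high dose as more than 20 mg/day, taken from criterion 3 and 5.3.2.

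The documents give no prevalence of such steroid use, so no count of affected patients can be supported. Existing glucose safeguards limit the consequence. Nobody should infer an effect on the efficacy conclusions: ORR, power and alpha do not depend on this rule. It is a minor eligibility and safety consistency correction, though more than a typographical one because it changes who may be enrolled.

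**What to change.** - Add to Section 4.2 an exclusion for patients who, at the time of first dose, are receiving systemic corticosteroids above 20 mg/day prednisone or equivalent for a condition that pre-dates informed consent. Keep criteria 2 and 3 as they are.
- Define high dose steroids in the synopsis by the same threshold.
- State in Section 5.3.2 whether an acute condition arising between consent and Day 1 falls under the limited-duration allowance, and keep the synopsis consistent with that answer.

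The cost is one criterion, one synopsis phrase and one clarifying sentence. No new data are needed: the screening history in Section 7.1 already covers concomitant medications, and SAP Section 7.6.5 already lists them by subject. The downside is that a few patients become ineligible. The new criterion acts only on patients not yet enrolled. The documents do not say whether enrollment is still open; if it is closed, the useful part is the wording alignment.
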